10.1. Schedule of Events

The point of enrollment is the time when a subject signs the ICF. At that point, the subject is considered included in the study.

Approximately 15 subjects indicated for pulmonary vein ablation will be enrolled in the study. Participants will be invited to attend the Baseline and Procedure visit. The baseline visit can be on the same day as the ablation procedure.

After signing the ICF, the subject will be prepared for the ablation procedure for which he/she was indicated. After the ablation procedure and before the testing of efficacy of this procedure, the study procedure will be performed. The expected duration of the study procedure is approximately 30 minutes. The study procedure will take place during the routine waiting period following the ablation procedure. Since this is an acute study no follow up is expected and a Study Exit form will be completed after the research procedure.

Subjects will be enrolled over a period of approximately 18 months. The results of the study are expected to be ready for internal review approximately 3 months after the last subject visit is completed.

Table 2 – Data collection

| Data Criteria | Baseline | Procedure | Exit |
|------------------------------|----------|-----------|------|
| Informed Consent | ✓ | | |
| Inclusion/Exclusion Criteria | ✓ | | |
| Demographics | ✓ | | |
| ECG | ✓ | | |
| BP | ✓ | | |
| Devices information | | ✓ | |

| | | | |
|---|--|---|---|
| Study procedure parameters (Impedance, Pacing threshold, Ventricular capture, safety test, PCL, mA) | | ✓ | |
| Exit / withdrawal CRF | | | ✓ |
| Adverse Events and Device Deficiencies | As they occur, assessed throughout the study | | |
| Deviations | | | |

10.2. Subject Consent

The investigator or authorized designee must obtain written informed consent before any clinical study related activity takes place.

Legally incompetent subjects will not be included in this study.

Well in advance of the consent discussion, the subject should receive the Medtronic and EC approved Subject Information and ICF. During the consent discussion, the investigator or his/her authorized designee must fully inform the subject of all aspects of the clinical study that are relevant to the subject's decision to participate in the clinical study. Patient is willing and able to sign the Informed Consent and to cooperate with study procedure. All items addressed in the Patient Information and the ICF must be explained. The language used shall be as non-technical as possible and must be understandable to the subject and the impartial witness, where applicable.

The subject must have ample time and opportunity to read and understand the Subject Information and the ICF, to inquire about details of the clinical study, and to decide whether or not to participate in the clinical study. All questions about the clinical study should be answered to the satisfaction of the subject.

Neither the investigator, nor the investigation site staff shall coerce or unduly influence a subject to participate or to continue to participate in the clinical study. The informed consent process shall not waive or appear to waive the subject's rights.

The sponsor will revise the written Subject Information and ICF whenever new information becomes available during the course of the study which are pertinent to the safety and well-being of the subject, as this could impact a subject's willingness to participate in the study. The revised information will be sent to the investigator for approval by the EC. After approval by the EC, a copy of this information must be provided to the new participating subjects. If relevant, approval may be requested from subjects already enrolled and exited to the study to inform them.

When the subject decides to participate in the clinical study, the ICF must be signed and personally dated by the subject and investigator or authorized designee. If applicable, the witness shall also sign and personally date the consent form to attest that the information in the Patient Information and ICF was accurately explained and clearly understood by the subject, and that informed consent was freely given.

After all persons have signed and dated the ICF, the investigator must provide the subject with a copy of the Subject Information and the signed and dated ICF.

The study specific Master ICF will be provided under a separate cover.

10.3. Assessment of Efficacy

During sinus rhythm, the number of cases in which the septal pacing electrodes are successfully placed in a stable position will be registered. A stable position is defined as a location where the atrial septal pacing threshold is lower than 10 mA at 1msec on all electrodes and where no ventricular capture at twice the atrial capture threshold is observed.

When the subject is in sinus rhythm after PV ablation, as a first step the atrial pacing threshold is determined, for each electrode, using a pulse width of 1 msec. Also, the impedance is determined for each electrode. During atrial stimulation at high threshold currents, ventricular capture may be possible and absence of ventricular capture at the atrial capture threshold measurement will be confirmed by stimulating from each electrode with twice the atrial capture threshold current (corresponding to specific electrode) from all electrodes at the same time using overdrive pacing at 20 bpm. If ventricular capture is observed during atrial stimulation at twice the atrial capture threshold, the position of the catheter on the septum will be changed and the tests for measuring thresholds, impedances and ventricular capture will be repeated until no ventricular capture occurs during atrial pacing at twice the atrial capture threshold. If it does not occur we will increase the current up to 20 mA and repeat sequence mentioned above. The maximum current will be that current, which does not induce ventricular capture when stimulating from all four electrodes at same time and is 20 mA or lower.

Next, atrial fibrillation will be induced by rapid atrial pacing, gradually elevating the atrial pacing rate until 1:1 atrial capture is lost. AF cycle length will be determined by recording the atrial electrogram on the septum. Stimulation on the septum from all electrodes starts at the current defined above, using various pacing cycle length (PCL), being percentages of AFCL and will last for 10 to 30 seconds, depending on when capture occurs, followed, if feasible, by slow pacing using an interval of 130% of AF for one cycle followed by 1.5 second of 180% of AF Cycle length at maximum output which did not induce ventricular capture (20 mA or lower). Multiple PCLs will be used to start the pacing sequence. During each stimulation sequence, corresponding to each PCL, atrial capture at each recording electrode will be assessed. The optimal parameters for stimulation will be used to determine local capture for all electrodes.

When the subject will still be in AF after successful pulmonary vein isolation the ventricular capture tests will be performed first during atrial fibrillation (as described above for subject in sinus rhythm). Then, AF cycle length will be determined and

the two-stage atrial pacing scheme as described above will be performed. If delivery of the two-stage atrial pacing scheme either will not be feasible or not stop the AF, the subject will be externally cardioverted under deep sedation as would have been done as common practice at the end of the ablation procedure. Next, during sinus rhythm pacing thresholds and impedances on all septal catheter electrodes will be determined.

To assess if the two-stage pacing scheme can terminate AF, the surface ECG will be analyzed and PCL and stimulation current will be noted.

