One reason why clinical studies are often non-conclusive, could be that they focus on AF frequency and burden, but few of them are aimed at evaluating the effect of AF pacing on the atrial tissue.⁹ More detail can be found in animal and human mapping experiments: although termination of AF by rapid pacing was not observed, the possibility of creating an area of local capture of the atrial tissue by rapid pacing of AF has been demonstrated.¹⁰⁻¹⁴ To overcome the limitations of human and animal experiments, a computer model of AF has been used to systematically simulate all existing ATP algorithms on AF and test all pacing locations.¹⁵ This systematic model-based testing of site rapid pacing of AF revealed that the septum was the only pacing site that yielded sporadic AF capture episodes in both atria, but this in general did not result in AF termination or permanent changes in AF patterns. Based on this result, a new dual-stage septal pacing has been developed in the computer model: rapid pacing was applied from the septal area following a dual-stage scheme: 1) rapid pacing for 10-30 s at pacing intervals 62-70% of AF cycle length (AFCL), 2) slow pacing for 1.5 s at 180% AFCL, initiated by a single stimulus at 130% AFCL.¹⁶ The proposed septal pacing algorithm could suppress AF reentries in a more robust way than classical single site rapid pacing and at an optimal pacing cycle length (64% AFCL) up to 29% of AF termination was observed in the computer model¹⁶. Septal pacing of AF is therefore proposed here as a simple and attractive approach since it may produce simultaneous bi-atrial stimulation using a single lead, without the need of complex methods for synchronizing multiple pacing sites.

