5.2.2. Secondary Endpoint(s)

To assess Localized Atrial Capture the following endpoints will be considered:

- The number of AF episodes in which local capture is recorded during atrial septal stimulation in at least one of the electrode positions
- The number of electrodes for which local capture is determined using pacing schemes with various pacing cycle lengths (PCL) for a duration of 10-30 seconds depending on when capture occurs, at the start of the scheme followed, if feasible, by slow pacing for 1.5 s at 180% AFCL, initiated by a single stimulus at 130% AFCL.
- The spatial extend of capture (assessed from the atrial electrograms recorded from the multipolar right atrial catheter and the multipolar coronary sinus catheter) to obtain local atrial capture obtained with septal pacing of AF, will be assessed off-line after the study procedure.

To assess whether AF termination can be obtained using a dual-stage septal pacing scheme, the surface ECG will be analyzed and the PCL and stimulation current used will be noted to measure the number of subjects in which the pacing scheme successfully terminates the AF episode.

6. Study Design

The AF Septal Pacing study is a non-randomized, non-controlled, acute, single-arm research study that will be conducted in up to three European centers.

Approximately 15 subjects with AF indicated for ablation of the pulmonary vein will be enrolled in the study. Participants will attend the Baseline visit and the Procedure visit. The baseline visit can be on the same day as the ablation procedure. Since it is an acute study, no follow-up visit will occur. The research procedure will be performed during an already scheduled ablation procedure. Subjects will be enrolled over a period of approximately 18 months.

The point of enrollment is the time when subject signs and dates the Informed Consent Form (ICF). At that point, the subject is considered included in the study.

Selection of subjects, treatment of subjects, and evaluation of study data are potential sources of bias. Methods incorporated in the study design to minimize potential bias include (but are not limited to):

- Patients will be screened to confirm eligibility for enrollment in accordance to the inclusion/exclusion criteria.
- Subject demographics will be collected at baseline on possible differences that may affect the primary objective.

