| Monitoring system. | Could be e.g. a stationary Bard EP recording system, a physiological recorder, such as the porti-system (TMSI) or any other electrophysiological monitoring system used in EP lab during the ablation procedure. | CE marked | Monitoring (one per site) | NO (CE marked used within approved indications) |

Pacing system: A clinical electrophysiological stimulator will be used to deliver the dual stage septal pacing protocol to pace and potentially terminate atrial fibrillation. The stimulator should offer four independent pacing channels, to be able to independently stimulate the four electrodes of the interatrial septal catheter. If no four-channel electrophysiological stimulator is available at the clinical study site, study site can request Medtronic reimburse a commercially available four channel electrophysiological stimulator (St. Jude Medical – EP4-Stimulator). The provided stimulator is to be used in accordance with this Clinical Investigation Plan and for this study only.

Pacing catheters: A multipolar (decapolar) Lasso catheters will be used to pace the interatrial septum. In acute animal studies, a Biosense-Webster Lasso Catheter was successfully used²³. Therefore, it is preferable to use the Lasso catheter in this study unless experiences in this human study support the use of another Lasso catheter such as the Achieve. The decapolar Lasso or Achieve catheter will be used according to standard clinical practice.

Monitoring Catheters: Standard electrophysiological recording according to standard clinical practice during AF ablation will be used. This includes the use of a decapolar coronary sinus (CS) electrophysiological recording catheter, and the use of a decapolar right atrial (RA) electrophysiological recording catheter.

Monitoring System: Atrial electrocardiograms will be recorded throughout the study procedure. Intra-atrial electrocardiograms will be recorded from the right atrial decapolar catheter, the coronary sinus catheter and the interatrial septal catheter. All signals will be recorded on the available electrophysiological recording system.

The products needed are already available at the site as standard material used for the routine clinical ablation procedure, for which the patient is indicated and referred to the site.

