9.2. Site activation

Before performing study related activities, all requirements shall be fulfilled, including, but not limited to the following:

- EC approval (and voting list, as required by local law) of the current version of the CIP and ICF.
- Regulatory Authority approval or notification (as required per local law)
- Fully executed Clinical Trial Agreement (CTA)
- Curriculum Vitae (CV) of investigators and key members of the investigation site team

- Documentation of delegated tasks
- Documentation of study training.

Additional requirements imposed by the EC and Regulatory Authority shall be followed, as appropriate.

Medtronic may distribute pre-populated study-specific ISF and will provide site with documentation of study site/investigator readiness. Evidence of site/investigator readiness must be received prior to subject enrollment and must be filed in the ISF.

10. Study Procedures

Baseline:

Patients will be pre-screened for potential enrolment in the clinical investigation by evaluating if the patients meet the inclusion and exclusion criteria. Next the patient is asked for her or his informed consent. A patient is considered an enrolled subject after he/she has personally signed and dated the ICF. At baseline, subject characteristics will be noted such as age, gender, weight, height, AF status and AF history.

Enrolled subjects will undergo the AF ablation procedure, for which they have been referred to the center. For this standard procedure, the subject will be prepared as per standard catheterization/EP procedures, which includes administration of anesthesia/analgesia, ECG and BP monitoring.

Procedure:

The subject will be sedated. A trans-septal puncture will be made to access the left atrium and place a septal catheter and the clinically used ablation catheter. One decapolar recording catheter will be placed in the right atrium and one decapolar recording catheter will be placed in the coronary sinus. Both decapolar catheters are used according to standard clinical practice. The standard procedure workflow is visualized on the left side of figure 1 below.

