After successful pulmonary vein isolation, there is a routine waiting time of half an hour to confirm efficacy of the ablation procedure. During this waiting period, the study procedure will be performed. The deviations from the standard procedure are indicated in orange on the right of figure 1 below. The septal catheter, already in place in the right atrium, will be positioned on the left interatrial septum via a trans-septal approach. In most cases the patient will be in sinus rhythm. In these cases, during sinus rhythm pacing thresholds and impedances on all septal catheter electrodes will be determined. Also, potential ventricular capture will be assessed. Next, atrial fibrillation will be induced by rapid atrial pacing. AF cycle length will be determined, during 1 minute of atrial fibrillation using the ablation catheter electrodes. Subsequently, the rapid pacing phase of the two-stage atrial pacing scheme will be applied to four septal electrodes at same time during half a minute using the quadripolar electrophysiological stimulator (e.g. EP4 stimulator). An electrophysiological recording system (already in place for the AF ablation procedure), recording all atrial electrograms, will be used to assess the study

[figure not shown]
outcome of local atrial capture. In addition, if feasible, AF termination will be evaluated using the two-stage pacing algorithm. If needed cardioversion will be used to terminate AF.

In a minority of cases the subject will still be in AF after successful pulmonary vein isolation. In these cases, the ventricular capture tests as described above will be performed first, then AF cycle length will be determined, and the two-stage atrial pacing scheme as described above will be performed. If delivery of the slow pacing phase of the two-stage atrial pacing scheme either will not be feasible or not stop the AF, the subject will be externally cardioverted under deep sedation as would have been done as common practice at the end of the ablation procedure. Next, during sinus rhythm pacing thresholds and impedances on all septal catheter electrodes will be determined.

[figure not shown]
Protocol deviations from what is stated above will be documented.

Figure 1: Study steps to be added to standard procedure.

STANDARD ABLATION PROCEDURE

AF SEPTAL PACING STUDY DURING STANDARD ABLATION PROCEDURE

*Patient is under deep sedation for whole procedure
§ If subject is still on AF

No follow-up data will be requested for the study.

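### The source of the AF cycle length is stated inconsistently and not recorded, so the AFCL that scales every pacing interval may come from different sites in different subjects

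*Protocol*

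**What the plan says.** For subjects in sinus rhythm after isolation, AF is induced and AFCL is then measured. The protocol describes this measurement in two ways:

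- Synopsis and Section 10 (Study Procedures): "AF cycle length will be determined, during 1 minute of atrial fibrillation using the ablation catheter electrodes". No anatomical site is given.
- Section 10.3: "AF cycle length will be determined by recording the atrial electrogram on the septum". No catheter and no recording time are given.

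For subjects still in AF, 10.3 says only "Then, AF cycle length will be determined and" and moves on to the pacing scheme. The Synopsis and Section 10 are equally silent on the source for this pathway.

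The two catheters are separate devices: the trans-septal puncture is used to "place a septal catheter and the clinically used ablation catheter". Section 7.1 lists the study recordings: "Intra-atrial electrocardiograms will be recorded from the right atrial decapolar catheter, the coronary sinus catheter and the interatrial septal catheter". The ablation catheter is not in that list.

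AFCL then sets the stimulation. Section 10.3 has rapid pacing "using various pacing cycle length (PCL), being percentages of AFCL and will last for 10 to 30 seconds", and 5.2.2 has it followed, where feasible, "by slow pacing for 1.5 s at 180% AFCL, initiated by a single stimulus at 130% AFCL".

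The SAP summarises AFCL in ms in results Table 3. In 8.7.2 it lists atrial cycle length among the subgroups for describing capture and termination. Tables 5 and 6 each carry one AFCL field, with StudyProc as its form.

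**The concern.** A centre working from Section 10 and a centre working from 10.3 could both follow the protocol and still take AFCL from different places. The programmed pacing interval, the AFCL summary and the cycle-length subgroup would then rest on a quantity that does not mean the same thing in every subject.

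The mixing need not be random. The 10.3 sentence about the septum sits in the induced-AF pathway, while the still-in-AF pathway names no source. The SAP describes results by centre (8.7) and by SR versus AF group (8.7.2). A difference in AFCL, or in capture by cycle length, between such groups could partly reflect where AFCL was measured. With about 15 subjects in up to three centres, a few inconsistent cases would show in the descriptive results.

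**Working it through.** **Step 1. The statements side by side.**

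| Place | Catheter | Site | Duration |
|---|---|---|---|
| Synopsis; Section 10, induced AF | Ablation | Not stated | 1 minute |
| 10.3, induced AF | Not stated | Septum | Not stated |
| Synopsis; Section 10; 10.3, still in AF | Not stated | Not stated | Not stated |

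No row is complete, and none gives an averaging rule.

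**Step 2. Does the SAP or the data collection settle it?** The data lists in Protocol Table 2 and Section 10.5 name PCL but neither AFCL nor its source. SAP Table 5 (from the CRF) has AFCL without a source. Table 6 is the Matlab table, but its AFCL field is still attributed to StudyProc; only the sensing and capture fields are attributed to Matlab. SenseCatheter in Table 6 (CS, RA or Septal) identifies where capture was sensed, not where AFCL was measured. No offline AFCL computation is specified.

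**Step 3. What depends on AFCL?** The programmed rapid interval, the 130% and 180% slow intervals, the AFCL summary and the cycle-length subgroup all do. The primary endpoint does not: it uses a threshold below 10 mA at 1 msec and absence of ventricular capture. Capture (temporal association of signal and stimulus) and termination (rhythm change) are also defined without AFCL.

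**Step 4. Illustration of sensitivity.** The plan has no figure to reproduce, since it makes no sample size or power calculation. Inputs:

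- 64% is the optimal pacing cycle length in the computer model, and 62-70% is the model's range (Protocol 4.1).
- A1 is the AFCL used to set the interval, and A2 is the AFCL from the other recording.
- d = A2/A1 - 1 is **assumed**, because the documents give no between-site difference.

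Formula: interval as a percentage of A2 = 64 / (1 + d).

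| d | Percentage of A2 |
|---|---|
| -10% | 71.1 |
| -5% | 67.4 |
| -3% | 66.0 |
| 0 | 64.0 |
| +3% | 62.1 |
| +5% | 61.0 |
| +10% | 58.2 |

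The model's limits are reached at:

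- lower limit: 64/62 - 1 = +3.2%
- upper limit: 64/70 - 1 = -8.6%

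Taking A2 as the base gives the same limits as 62/64 - 1 = -3.1% and 70/64 - 1 = +9.4%.

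In milliseconds, the limits depend on AFCL. Over the 100 to 400 ms that SAP Tables 5 and 6 allow for the field, +3.2% is 3.2 to 12.9 ms and -8.6% is 8.6 to 34.3 ms. At an assumed 200 ms they are about 6.5 and 17.1 ms.

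**The case against.** The strongest reply is that the passages do not contradict each other. Section 10 names a catheter and 10.3 names a site, and an ablation catheter held on the septum would satisfy both. That stands. A reader might infer two competing definitions of AFCL, but the text establishes only an incomplete and ambiguous one. The recording list in 7.1 suggests that 10.3 means the septal catheter, but 10.3 does not say so. Nor does the list prove that the ablation signal goes unrecorded, since 7.1 and Section 10 also speak of all signals and all atrial electrograms.

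A reader might also infer that pacing runs would be misclassified as inside a 62-70% window. The documents do not support this. The range describes the computer model; the current protocol specifies various percentages of AFCL and sets no window, and no SAP field labels a run by one. The SAP has no PCL/AFCL ratio variable either: it stores AFCL and the paced interval separately in ms.

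Finally, the study is descriptive, tests no hypothesis and plans no statistical comparison between groups, so no inference is at risk. Septal, RA and CS electrograms are recorded throughout, so AFCL could be recovered later. This limits the damage, but recovery is possible only if someone decides to do it; the plan does not call for it.

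**Conclusion.** The point holds as an unreconciled and incomplete measurement definition, with no field in the data tables to show which source was used. It affects the programmed percentages, the AFCL summary and the cycle-length subgroup, all of which belong to descriptive secondary results. The primary endpoint and the definitions of capture and termination are untouched.

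The actual size is unknown. The 3.2% and 8.6% limits show how little disagreement would move a nominal 64% outside the model's range. They are not estimates of a between-site difference and do not show that any run would be mislabelled. The conclusion assumes that at least some centres or pathways would use different recordings, which the text permits but does not require.

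**What to change.** 1. Reconcile the Synopsis, Section 10 and Section 10.3 to one stated catheter, site, recording duration and averaging rule, covering both the induced-AF and the still-in-AF pathways. Which recording sets the pacing interval is for the sponsor to decide.
2. Add an AFCL-source field to SAP Tables 5 and 6, separate from SenseCatheter.
3. For analysis, compute AFCL offline in every subject from one common electrode set that is already recorded (for example the septal catheter), over a stated segment of AF before pacing. Use this value for the AFCL summary, the cycle-length subgroup and any PCL reported as a percentage of AFCL. Keep the value used during the procedure alongside it, so that the programmed percentage stays traceable.

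The cost is a few sentences, one data field and a short offline computation on recordings that the study already collects. The offline value cannot change the interval that was delivered, but it makes its description comparable across subjects and centres.
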